9.4.2 Joint Evaluation

Anatomical joints are evaluated for swelling and tenderness at every study visit. The 34 anatomical joints in [Table 11](#) are assessed in this study for both the left and right side of the body.

Table 11. Anatomical Joints Assessed for Calculation of Tender and Swollen Joint Counts (TJC68 and SJC66)

Temporomandibular	Sternoclavicular	Acromio-clavicular	Shoulder
Elbow	Wrist	Metacarpophalangeal I	Metacarpophalangeal II
Metacarpophalangeal III	Metacarpophalangeal IV	Metacarpophalangeal V	Thumb Interphalangeal
Proximal Interphalangeal II	Proximal Interphalangeal III	Proximal Interphalangeal IV	Proximal Interphalangeal V
Distal Interphalangeal II	Distal Interphalangeal III	Distal Interphalangeal IV	Distal Interphalangeal V
Hip ^a	Knee	Ankle	Tarsus
Metatarsophalangeal I	Metatarsophalangeal II	Metatarsophalangeal III	Metatarsophalangeal IV
Metatarsophalangeal V	Great Toe/Hallux	Interphalangeal II	Interphalangeal III
Interphalangeal IV	Interphalangeal V		

a Hip joints are not assessed for swelling.

At each study visit, a joint evaluator assessed whether a particular joint was "tender or painful" where presence of tenderness was scored as "1" and the absence of tenderness was scored as "0," provided the joint was not replaced ("9") or could not be assessed ("NA") due to other reasons (e.g., post-corticosteroid joint injection). The total tender joint count (TJC68), which is based on 68 joints, will be derived as the sum of all "1s" and proportional extrapolation will be used to impute joint counts for the joints that are replaced or not assessed. A similar method will be followed for the derivation of total swollen joint count (SJC66), which is based on 66 joints as the hip joints are excluded. Thus, the range for TJC68 will be 0 to 68 and 0 to 66 for SJC66.

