concomitant use of up to 2 csDMARDs except the combination of MTX and leflunomide; see Inclusion Criterion 3) is allowed as per local label. Starting at Week 24 and thereafter, intra-articular, intramuscular, intravenous, trigger point or tender point, intra-bursa, and intra-tendon sheath injections of corticosteroids, dosage and frequency per standard of care, are allowed. However, joint injections should be avoided within 21 days prior to the next scheduled study visit to avoid confounding effects of systemic absorption of intra articular corticosteroids. For the analysis of the TJC and SJC, injected joints will be considered "not assessable" for 3 months from the time of the intra-articular injection. Also, per investigator's judgment, background RA therapies (corticosteroids, NSAIDs, acetaminophen, csDMARDs) can be adjusted for each subject beyond Week 24 until end of Period 2. For RA flare treatment, no more than 3 consecutive days of high-dose systemic corticosteroids (maximum dose of 0.5 mg/kg/day of prednisone or its equivalent) is allowed, after which subject should resume their usual daily oral corticosteroid dose.

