#### **Corticosteroids**

Oral corticosteroids (> 10 mg prednisone/day or equivalent), intra-articular, intramuscular, intravenous, trigger point or tender point, intra-bursa, and intra-tendon sheath corticosteroids are NOT allowed up to Week 24.

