#### *SJC Assessment*

An assessment of 66 joints ([Appendix D](#)) will be done by directed physical examination at visits specified in [Table 2](#) and [Table 4](#). The joints to be examined for swelling are the same as those examined for tenderness, except the hip joints are excluded. Joint swelling will be classified as present ("1"), absent ("0"), replaced ("9") or no assessment ("NA").

Any injected joints will be considered as "not assessed" ("NA") for 3 months from the time of the intra-articular injection.

If possible, the TJC and SJC should be performed by an independent and blinded joint assessor who should not perform any other study related procedures.

In order to minimize variability, the same independent joint assessor should evaluate the subject at each visit for the duration of the trial as much as possible. A back-up independent joint assessor should be identified. The independent joint assessor should be a qualified medical professional (e.g., nurse, physician's assistant, physician). Any other joint assessor must be trained and competent in performing such assessments. It is the responsibility of the Investigator to ensure that all assessors are qualified and trained to perform joint assessments. If the independent assessor is not available, the pre-identified back-up assessor should perform such assessments.

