9.3 Long Term Efficacy Analysis

Assessments to evaluate long term efficacy will be analyzed for the following measures at Week 1, 2, 4, 8, 12, 16, 20, 24, 36, 48, and every 12 weeks thereafter until completion of the study.

- ACR20/50/70 response rates;
- Change from baseline in individual components of ACR response;
- Change from baseline in DAS28 (CRP);
- Change from baseline in DAS28 (ESR);
- Change from baseline in morning stiffness (severity and duration);
- Proportion of subjects achieving LDA and proportion of subjects achieving CR based on DAS28 (CRP), DAS28 (ESR), SDAI, and CDAI criteria;
- Proportion of subjects with no concomitant corticosteroid use (among subjects with corticosteroid use at baseline).

Assessments to evaluate long term efficacy will be analyzed for the following measures at Week 4, 12, 24, 48:

- Change from baseline in EQ-5D-5L;
- Change from baseline in FACIT-F;
- Change from baseline in RA-WIS.
- Change from baseline in SF-36.

Descriptive statistics will be provided for each randomized treatment group sequence as defined in Section 9.1.1. These include the number of observations, mean, standard deviation, 95% CI, median, minimum, Q1, Q3 and maximum for continuous endpoints; and frequencies and percentages with 95% CI using normal approximation for binary endpoints. Plot for each randomized treatment group sequence over time will be provided up to Week 36 and 48.

No missing data imputation will be applied. All efficacy analyses will be based on As Observed (AO) analysis.

Table 10 below provides the overview of the long term efficacy analyses to be performed on different endpoints.

Table 10. Summary of Efficacy Variables and Corresponding Analyses for Long Term Efficacy Analysis

Efficacy Variables	Analysis Method
Binary Endpoints:	

 • ACR20/50/70 response by visit • LDA and CR based on DAS28 (CRP), DAS28 (ESR), SDAI, and CDAI criteria by visit • Proportion of subjects with no concomitant corticosteroid use (among subjects with corticosteroid use at baseline) 	
 • Point estimate and 95% CI of the response rate for each randomized treatment group sequence • Plot for each randomized treatment group sequence over time • Imputation: AO • Analysis Set: FAS
Continuous Endpoints:	

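### From Week 24, proportional extrapolation counts a steroid-injected active joint as nearly resolved, which moves the descriptive long-term joint counts towards improvement

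*SAP*

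**What the plan says.** **When injections are possible.** In Protocol 5.2.3.3 (Corticosteroids), the list that ends "intra-tendon sheath corticosteroids are NOT allowed up to Week 24" also covers intra-articular injection. Protocol 5.2.3.2 then permits, at standard-of-care dosage and frequency, "Starting at Week 24 and thereafter, intra-articular, intramuscular, intravenous, trigger point or tender point, intra-bursa, and intra-tendon sheath injections of corticosteroids". It adds that "joint injections should be avoided within 21 days prior to the next scheduled study visit".

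**Status of an injected joint.** Protocol 5.2.3.2 sets an analysis rule: "For the analysis of the TJC and SJC, injected joints will be considered" not assessable for 3 months. Protocol 5.3.1.1 (SJC Assessment) repeats that such joints are NA "for 3 months from the time of the intra-articular injection".

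**How the gap is filled.** SAP 9.4.2 sums the joints scored 1, and "proportional extrapolation will be used to impute joint counts for the joints that are replaced or not assessed". Replaced joints (code 9) and joints that are NA after a steroid injection get the same treatment.

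**Where the counts are used.** SAP 9.3 summarises ACR20/50/70 and the ACR components through Period 2 and states that "All efficacy analyses will be based on As Observed (AO) analysis". SAP 9.1.1 makes this analysis descriptive, without testing. No rule carries an injected joint's earlier status forward or treats injection as an intercurrent event. SAP 9.4.6 to 9.4.8 use 28-joint counts and do not say how an NA joint enters them.

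**The concern.** Proportional extrapolation assumes that a missing joint resembles the assessed ones. That is reasonable for a replaced joint. A joint chosen for steroid injection is likely to have been tender or swollen, while most of the remaining 60 or so are not. Filling it with their average removes most of an active joint from the count.

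The situation will be routine wherever injections are used. After Week 24 the scheduled visits are 12 weeks (84 days) apart, and injections should avoid the 21 days before a visit. An injection therefore usually falls 21 to 84 days before the next visit, and the joint is normally still NA there.

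What is at stake is the reading of long-term joint counts and ACR responses by dose sequence. Protocol 5.6.1 says the fixed-dose extension is meant to allow better assessment of the three doses. The NA rule appears intended to keep local steroid effect out of the counts, but with this imputation it barely does so.

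**Working it through.** **Inputs.** N = 68 for TJC68 and 66 for SJC66 (SAP 9.4.2). Entry requires at least 6 swollen and 6 tender joints (Protocol 5.2.1). ACR needs the threshold improvement in both counts and in at least 3 of 5 non-joint measures (SAP 9.4.1). Joint counts in the examples are illustrative. Each injected joint is taken to be both tender and swollen.

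**Formula.** Derived count = (sum of 1s ÷ joints assessed) × N.

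**The plan's own figure.** With 60 joints assessed, all 0 gives 0, and all 1 gives 60/60 × 68 = 68 or 60/60 × 66 = 66. This agrees with the SAP: "the range for TJC68 will be 0 to 68 and 0 to 66 for SJC66".

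**Direction.** If m of k active joints are injected, the derived count is (k − m) × N/(N − m). This is below k whenever k < N. It depends on the injected joints being active: with a count of 10 and two inactive joints injected, SJC would rise to 10 × 66/64 = 10.31.

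**Main example.** Baseline 8/8, now 7/7, 2 active joints injected, nothing else changed since the last visit.

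| Treatment of the 2 joints | SJC66 | TJC68 | Improvement (SJC/TJC) |
|---|---|---|---|
| Pre-injection status kept | 7 | 7 | 12.5% / 12.5% |
| SAP extrapolation | 5 × 66/64 = 5.16 | 5 × 68/66 = 5.15 | 35.5% / 35.6% |
| Scored as resolved (0) | 5 | 5 | 37.5% / 37.5% |

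Under the SAP rule each injected joint contributes 5/64 = 0.08 to SJC and 5/66 = 0.08 to TJC, so the result lies close to scoring it resolved.

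**Near a threshold (joint part of ACR only).**
- Baseline TJC/SJC 14/12, now 12/10 (14.3%/16.7%). One injection gives 11 × 68/67 = 11.16 and 9 × 66/65 = 9.14, or 20.3%/23.8%. The ACR20 joint criteria are now met.
- Baseline 14/12, now 8/7 (42.9%/41.7%). One injection gives 49.3%/49.2%, not enough for ACR50. Two give 6 × 68/66 = 6.18 and 5 × 66/64 = 5.16, or 55.8%/57.0%, which is enough.

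**Away from a threshold.**
- Baseline 24/24, now 21/21 (12.5%), 2 injected: 19 × 66/64 = 19.59 and 19 × 68/66 = 19.58, both 18.4%. ACR20 is not met on joints.
- Counts unchanged from baseline: at 6 joints, 2 must be injected for the 20% threshold and 4 for 50%. At 20 joints, 6 and 12.

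**Non-joint condition.** If the five non-joint measures are unchanged from baseline, 0 of the required 3 are met, and no number of injections produces an ACR response.

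**The case against.** The strongest reply is that the joint's true status after injection is unknown. If the steroid worked, extrapolation is slightly conservative: 5.16 against 5.00 in the main example. Carrying the old score forward assumes no local benefit at all, which is the opposite extreme. This stands as far as it goes, and the SAP rule should not be described as overwriting a known active joint. But a gain from a local injection is not the effect of upadacitinib, and the protocol's decision to treat the joint as not assessable points the same way.

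A second reply is that carry-forward contradicts the protocol. It does not. The protocol says that the observed status is not used; it does not say what replaces it.

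Third, the data may not identify the injected joint. The medication record in Protocol 5.2.3 lists reason, dates, dose, route and frequency, but no joint site, and Appendix D has a single NA code without a reason. This is a real limitation but a workable one: replaced joints have their own code, and injection route and dates are recorded.

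Fourth, background csDMARDs, oral steroids and NSAIDs may also change from Week 24, so long-term response is never attributable to dose alone. That is true. It does not justify adding an avoidable artefact to the joint count itself.

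A reader might also infer that injections alone can create ACR20 or ACR50 responses. The 3-of-5 condition rules that out. The pool for ACR20 is smaller still, because subjects below 20% improvement in both counts at two consecutive visits must leave. The documents do not say whether extrapolated counts are used for that decision.

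**Conclusion.** The point holds within limits and should be corrected. SAP 9.4.2 gives injected active joints nearly full credit for resolution, so long-term TJC68 and SJC66 changes move towards improvement relative to pre-injection status: 35.5% against 12.5% in the main example. ACR20/50/70 can change only in subjects who already meet 3 of the 5 non-joint measures at that threshold and fail on joints alone.

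This assumes that injected joints were active and that the next visit falls within 3 months of injection.

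Two stronger readings are not supported. One is that the primary or Week 12 results are affected: injections are barred up to Week 24, so, protocol deviations aside, they are not. The other is that differences between 7.5, 15 and 30 mg are pulled together. That is plausible if a less effective dose attracts more injections, but injection frequency is not given overall or by dose, so neither this nor the effect on response rates can be sized. Nor do the documents say that the 28-joint indices are extrapolated; they are silent.

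**What to change.** In SAP 9.4.2:
- Keep proportional extrapolation for replaced joints and for joints unassessable for other reasons.
- For a joint that is NA because of an intra-articular injection within 3 months, carry forward its last pre-injection tender and swollen scores in TJC68 and SJC66. At minimum, pre-specify this as a sensitivity analysis shown beside the extrapolated result.
- State how such joints are identified: for example, coded NA rather than 9 at a visit within 3 months of a recorded intra-articular injection.
- Apply the same rule to the 28-joint counts in DAS28, SDAI and CDAI, for which no NA handling is stated.

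In SAP 9.3, add the number of subjects with injected joints by visit and dose. Protocol 5.3.3.2 lists intra-articular injections as a Period 2 measure, but SAP 9.3 plans only the proportion free of corticosteroid among baseline users.

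The cost is SAP wording and one derivation from joint scores and medication dates; where the joint site is not recorded, some NA joints may be misclassified. The downside is that carry-forward assumes no local benefit for 3 months, so long-term response rates become slightly less favourable. Period 1 derivations do not change.

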9.4.3 Patient's Global Assessment of Disease Activity Visual Analog Scale (VAS)

The subject will assess his/her disease activity for the past 24 hours using a Patient's Global Assessment of Disease VAS. The range is 0 to 100 mm with no activity being indicated by 0 and severe activity by 100.

9.4.4 Physician's Global Assessment of Disease Activity Visual Analog Scale (VAS)

The physician will assess Patient's disease activity at the time of visit using a Physician's Global Assessment of Disease VAS. The range is 0 to 100 mm with no activity being indicated by 0 and severe activity by 100.

9.4.5 Patient's Global Assessment of Pain

The subject will assess his/her pain in the previous week using a Patient's Global Assessment Pain VAS. The range is 0 to 100 mm with no pain being indicated by 0 and severe pain by 100.

9.4.6 Disease Activity Score (DAS28)

DAS28 (CRP) and DAS28 (ESR) are composite indices to assess disease activity in RA patients using hsCRP or ESR measurement respectively. The DAS provides a score between 0 and 10, indicating how active the rheumatoid arthritis is at the time of measurement.

DAS28 (CRP) and DAS28 (ESR) can be calculated based on Tender Joint Count, Swollen Joint Count, Patient's Global Assessment of Disease Activity (PtGA) (in mm), and hsCRP (in mg/L) or ESR (mm/hr).

$$\text{DAS28 (CRP)} = 0.56 \times \sqrt{(\text{TJC28}^*)} + 0.28 \times \sqrt{(\text{SJC28}^{**})} + 0.36 \times \ln(\text{hsCRP}\& + 1) + 0.014 \times \text{PtGA} \gg + 0.96$$

$$\text{DAS28 (ESR)} = 0.56 \times \sqrt{(\text{TJC28}^*)} + 0.28 \times \sqrt{(\text{SJC28}^{**})} + 0.70 \times \ln(\text{ESR}\#) + 0.014 \times \text{PtGA} \gg$$

* TJC28 refers to the Subject's total Tender Joint Count out of the provided 28 evaluated joints.

** SJC28 refers to the Subject's total Swollen Joint Count out of the provided 28 evaluated joints.

& hsCRP refers to the high-sensitivity c-reactive protein lab value. hsCRP unit in the DAS28 (CRP) equation is expressed as mg/L.

ESR refers to the Erythrocyte sedimentation rate. ESR unit in the DAS28 (CRP) equation is expressed as mg/hr.

» PtGA refers to the Patient's Global Assessment of Disease Activity.
where $\sqrt{\cdot}$ is square root and \ln is natural log.

Table 12. Anatomical Joints for DAS28 (CRP) Calculation

Shoulder	Elbow	Wrist	Thumb Interphalangeal
Metacarpophalangeal I	Metacarpophalangeal II	Metacarpophalangeal III	Metacarpophalangeal IV
Metacarpophalangeal V	Proximal Interphalangeal II	Proximal Interphalangeal III	Proximal Interphalangeal IV
Proximal Interphalangeal V	Knee		

To calculate observed DAS28 scores, the observed component value will be calculated first. Then the components will be included in the calculation per the DAS formula selected. If any observed component is missing in a window, then the observed DAS28 score will be missing.

9.4.7 Simplified Disease Activity Index (SDAI)

SDAI is a composite continuous index to assess disease activity based on TJC28, SJC28, Patient's Global Assessment of Disease Activity (PtGA) (in cm, 0 – 10), Physician's Global Assessment of Disease Activity (PhGA) (in cm, 0 – 10) and hsCRP (mg/dL). It can be derived as follows:

$$\text{SDAI} = \text{TJC28} + \text{SJC28} + \text{PtGA (cm)} + \text{PhGA (cm)} + \text{hsCRP (mg/dL)}.$$

To calculate observed SDAI scores, the observed component value will be calculated first. Then the components will be included in the calculation per the SDAI formula selected. If any observed component is missing in a window, then the observed SDAI score will be missing.

9.4.8 Clinical Disease Activity Index (CDAI)

CDAI is a composite continuous index to assess disease activity without using hsCRP measurement. It can be calculated based on TJC28, SJC28, Patient's Global Assessment

of Disease Activity (PtGA) (in cm, 0 – 10) and Physician's Global Assessment of Disease Activity (PhGA) (in cm, 0 – 10). It can be derived as follows:

$$\text{CDAI} = \text{TJC28} + \text{SJC28} + \text{PtGA (cm)} + \text{PhGA (cm)}.$$

To calculate observed CDAI scores, the observed component value will be calculated first. Then the components will be included in the calculation per the CDAI formula selected. If any observed component is missing in a window, then the observed CDAI score will be missing.

9.4.9 Clinical Remission (CR) and Low Disease Activity (LDA)

Clinical remission (CR) and low disease activity (LDA) based on DAS28 (CRP), DAS28(ESR), SDAI and CDAI are defined as follows:

	DAS28 (CRP) and DAS28 (ESR)	SDAI	CDAI
LDA	≤ 3.2	≤ 11.0	≤ 10
CR	< 2.6	≤ 3.3	≤ 2.8

9.4.10 ACR/EULAR Boolean Remission

ACR/EULAR Boolean remission is defined based on the following four criteria:

- Tender joint count ≤ 1 (based on 28 joints)
- Swollen joint count ≤ 1 (based on 28 joints)
- CRP ≤ 1 mg/dL
- Patient global assessment of disease activity ≤ 10 (mm)

All four criteria must be satisfied at a visit for a subject to be classified as achieving ACR/EULAR Boolean remission.

9.4.11 Disability Index of Health Assessment Questionnaire (HAQ-DI)

HAQ-DI is a self-reported patient outcome measurement. It is calculated as the mean of the scores from 8 following categories with a range 0 – 3: Dressing and Grooming, Rising, Eating, Walking, Hygiene, Reach, Grip, and Activities. The higher the score, the more likely to associate with morbidity and mortality for the RA patient.

The maximum score for all the questions in each category is considered as the score for the category. The Standard disability index (HAQ-DI) takes into account the subject's use of aids or devices or assistance in the scoring algorithm for a disability category. For each of the eight disability categories there is an AIDS OR DEVICES companion variable(s) that is used to record the type of assistance, if any, a subject uses for his/her usual activities. If aids or devices and/or assistance from another person are checked for a disability category, the score for this category is set to 2 (much difficulty), if the original score is 0 (no difficulty) or 1 (some difficulty). The HAQ-DI is then calculated by summing the adjusted categories scores and dividing by the number of categories answered. The HAQ-DI cannot be calculated if the patient does not have scores for at least 6 categories.

9.4.12 EuroQoL-5D (EQ-5D-5L)

EQ-5D is a standardized measure of health status developed by the EuroQol Group in order to provide a simple, generic measure of health for clinical and economic appraisal. The EQ-5D consists of 2 pages. The first page measures 5 dimensions of the health status (mobility, self-care, usual activities, pain/discomfort, and anxiety/depression) with 5 levels per dimension (no problems, slight problems, moderate problems, severe problems, and extreme problems corresponding to Level 1 to Level 5 respectively). The second page is an EQ Visual Analogue Scale (EQ VAS). EQ-5D health states, defined by the EQ-5D-5L descriptive system on the first page, may be converted into a single index value. The change from baseline of the index value and EQ VAS will be analyzed and reported. UK scoring algorithm will be used.

9.4.13 Form SF-36v2

The 36-Item Short Form, Version 2 (SF-36v2) Questionnaire with 4 week recall will be completed by the subject at Baseline, Weeks 4 and at study completion (Week 12 or at PD). The SF-36v2 health survey consists of 36 general health questions and this study is using the form for 4 weeks recall period (standard form). It has 2 components: physical and mental. For each component, a transformed summary score is calculated using 8 sub-domains: physical functioning, role-physical, bodily pain, general health, vitality, social functioning, role-emotional, and mental health.

The coding and scoring for the SF-36 will use the software provided by QualityMetrics.

9.4.14 Functional Assessment of Chronic Illness Therapy-Fatigue (FACIT-F)

Fatigue is one of the most frequent complaints of the elderly and is strongly associated with loss of independence and decreased physical activity and functional decline.

One validated tool to measure fatigue is FACIT Fatigue Scale v4. The FACIT Fatigue Scale is a short, 13-item, easy to administer tool that measures an individual's level of fatigue during their usual daily activities over the past week. Each of the fatigue and impact of fatigue items are measured on a four point Likert scale. The FACIT Fatigue Scale is ranged from 0 to 52 and the higher the score, the better the quality of life.

Score for each item is calculated by either subtracted from 4 or adding 0 depending on whether it is a reversal item or not. FACIT Fatigue Scale is then calculated by adding up all item scores, multiplied by 13 and divided by the number of items answered. It is essentially a prorated subscale if there are missing values for some items. If less than or equal to 50% of the items are answered (e.g., 6 out of 13), the proration is not acceptable and the scale will not be computed.

